9.2. Discontinuations, Lost to Follow-up, and Unscheduled Visits

All assessments of efficacy and safety done after discontinuation of study drug will be included in primary efficacy and safety analyses, for subjects who permanently discontinue study product, do not withdraw consent, and continue in the study.

If a subject withdraws consent, their last regularly scheduled study visit before withdrawing consent will be their last visit for efficacy and safety assessments.

If a subject is lost to follow-up, their last regularly scheduled study visit that they attended will be considered their last visit.

Efficacy assessments done at Unscheduled Visits and Possible PEx visits will be counted in efficacy analyses, only if AUQ-R at that visit indicates that the subject is having a PEx that meets primary or secondary definitions of a new PEx. Otherwise, efficacy assessments done at unscheduled visits and Possible PEx visits will be included only in listings.

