5.1.1. Primary Definition of New Pulmonary Exacerbation

The derivation for new PEx by the primary definition is provided below. The rules for defining new antibiotics used for new PEx, including the start and stop days, are also provided below.

Primary definition of new PEx:

- Physician diagnosis of PEx
- Prescription of new antibiotics for PEx
- Start date of new antibiotics for PEx is > 28 days after the stop date of any antibiotics given for any previous PEx. The physician does not need to determine if there is > 28 days from last use of antibiotics to the new antibiotics for PEx analysis purposes. The > 28-day gap will be determined centrally
- A new PEx is not defined by the number of antibiotics prescribed or the order or route of administration of the antibiotics (oral or IV) for that new PEx
- ≥ 4 out of 12 Fuchs criteria are met

New antibiotics for PEx

- Must be given for PEx

- Must be administered by oral or IV route
- Start date is day the physician prescribes that the subject should take this antibiotic treatment for a PEx
- Stop date is the last day the physician prescribes that the subject should take this antibiotic treatment for a PEx
- Start day > Day 1
- Start day \leq Day of Visit 8 or discontinuation from the study
- Regularly given prophylactic inhaled, oral, or IV antibiotics do not count as new antibiotics unless the dose is increased or given early for a PEx

Start day of a new PEx:

The first day that the physician prescribes that the subject should take any new antibiotic treatment for that new PEx

Stop day of a new PEx:

The last day that the physician prescribes that the subject should take any new antibiotic treatment for that new PEx or day of discontinuation from the study, whichever is sooner

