8.2. Study Treatments

8.2.1. Extent of Exposure

Treatment exposure duration will be defined as the number of days that the subject was exposed to study treatment as calculated using the formula:

$$\text{Exposure duration (days)} = \text{date of last dose} - \text{date of first dose} + 1.$$

Last dose date will be imputed using last contact date during active treatment for the subjects lost to follow up and as the date of the last visit seen, excluding safety follow-up visit, for subjects missing last dose date.

The duration of exposure will be summarized for treatment cohorts and combined lenabasum cohort. All summaries will be based on the safety population. Summary statistics will be presented for treatment exposure.

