9.4. Primary Efficacy Analysis

9.4.1. Event Rate of New Pulmonary Exacerbations per Subject per 28 Weeks by Primary Definition

The primary efficacy endpoint is the event rate of new PEx per subject per 28 weeks using the primary definition (Sections [4.2.1](#) and [5.1](#)), for the comparison of lenabasum 20 mg BID cohort to the placebo cohort, in the mITT population, through Visit 8 (Week 28) which is the treatment period.

The event rate per subject per 28 weeks of new PEx will be compared between the lenabasum and placebo cohorts using a Poisson regression model with effects of treatment and log (subject treatment exposure duration), adjusting for baseline subject characteristics of site location (United States; other countries), number of new PEx requiring IV antibiotics in the previous year (1; 2; 3); FEV1 % predicted (< 70; \geq 70); and baseline CFTR-targeting medications use (Yes; No – taken concomitantly on Day 1, baseline), and based on the mITT population.

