13. CHANGES FROM PROTOCOL-STATED ANALYSES

- The randomization schedules were initially set up stratified by 1 or 2 versus 3 number of previous PEx requiring IV antibiotics in the previous year as per protocol version 1. Protocol version 3.1 states that the randomization is stratified by 1 versus 2 or 3 number of previous PEx requiring IV antibiotics in the previous year. However, the IWRS was not updated to reflect this change until after 185 subjects had been randomized. Therefore, the number of previous PEx is treated as a continuous variable in the model for the primary and secondary efficacy endpoints.
- The efficacy and safety analyses will generally be based on on-treatment, from start of treatment to end of the treatment period at Week 28. For subjects discontinuing the study early, the treatment period will end at time of discontinuation. The safety follow-up period will be summarized separately for the AEs.
- Additional analyses and methods for handling missing data due to COVID-19 have been incorporated as described in [Section 4.1.14](#), according to recommendations from the FDA COVID-19 related Guidance dated March 2020 and June 2020.
- Additional detail has been added to the SAP regarding the tertiary objectives to facilitate programming and analyses.
- Baseline CFTR-targeting medications use (Yes; No) was added to applicable statistical models.

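### For subjects who withdraw consent, Section 9.2 ends efficacy data at the last scheduled visit, while the PEx window and the exposure term end on other dates and no rule says which prevails

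*SAP*

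**What the plan says.** Several sections of the SAP fix where a subject's data end.

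- **Section 9.2, withdrawal of consent:** "their last regularly scheduled study visit before withdrawing consent will be their last visit for efficacy and safety assessments".
- **Section 9.2, lost to follow-up:** "their last regularly scheduled study visit that they attended will be considered their last visit". This sentence does not mention efficacy or safety assessments.
- **Section 9.2, last paragraph:** "Efficacy assessments done at Unscheduled Visits and Possible PEx visits will be counted in efficacy analyses, only if AUQ-R at that visit indicates" a PEx that meets the primary or secondary definition. Nothing exempts withdrawn or lost subjects.
- **Section 5.1.1:** a new antibiotic qualifies if its start day is no later than "Day of Visit 8 or discontinuation from the study". Section 13 agrees: "For subjects discontinuing the study early, the treatment period will end at time of discontinuation".
- **Section 8.2.1:** "Treatment exposure duration will be defined as the number of days that the subject was exposed to study treatment", computed as last dose minus first dose plus 1. For one group the end is imputed: "Last dose date will be imputed using last contact date during active treatment for the subjects lost to follow up".

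The Section 8.2.1 duration is the denominator of the primary rate (Section 4.2.1) and enters the primary Poisson model on the log scale (Section 9.4.1). The last dose date is also the censoring date for time to first PEx (Section 9.5.3).

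**The concern.** The numerator and denominator of the primary rate should cover the same stretch of follow-up. Here a PEx treated after the last scheduled visit and before consent is withdrawn counts under Section 5.1.1, but the withdrawal sentence in 9.2 excludes it. If dosing continued, the days in that gap stay in the exposure term either way. In the time-to-first analysis, a subject whose only PEx fell in the gap would be treated as event-free up to last dose.

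Consent does not require the cut. Section 4.1.13 already rules out assessments after withdrawal, whereas 9.2 sets the end before it. The affected stretch also matters for event capture: Possible PEx Visits (Section 4.1.3), which exist to document exacerbations, fall between scheduled visits. Two programmers could follow the SAP in good faith and derive different primary event counts.

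**Working it through.** **End dates side by side, subject who withdraws consent**

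| Rule | End date |
|---|---|
| 9.2, withdrawal sentence | last regularly scheduled visit before withdrawal |
| 9.2, last paragraph | no end date; qualifying PEx at unscheduled visits count |
| 5.1.1 and Section 13 | discontinuation from the study |
| 8.2.1, 9.4.1, 9.5.3 | last dose |

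The direction of the mismatch depends on when dosing stopped. If dosing ran past the last scheduled visit, applying the cut removes events but keeps their days. If dosing stopped before that visit, exposure ends first and the mismatch runs the other way. For lost subjects, exposure ends at the last contact during active treatment. If that contact was the last scheduled visit, the dates coincide.

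**Inputs from the SAP**
- Section 6.3: 166 per main arm, about 15% dropout, placebo rate 0.80 per 28 weeks, rate ratio 0.65, so active rate 0.80 × 0.65 = 0.52.
- Section 4.1: visits every 4 weeks, so the gap is at most about 28 days, or 14 on average with random timing.
- Section 4.2.1: 28 weeks = 196 days.

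**The plan's own figure.** With 166 × 0.85 = 141 per arm, SE of the log rate ratio = √[(1/0.80 + 1/0.52)/141] = 0.150. Power = Φ(0.431/0.150 − 1.96) = 81.9%, which agrees with the stated 80%. The rates are therefore read correctly as per 28 weeks.

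**Assumptions not in the SAP.** Dropout at day 98, dosing continued to withdrawal, and every dropout subject to the 9.2 cut. The last is an upper bound, because Section 4.1.13 lists many other reasons for discontinuation.

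**Constant rate, 15% dropout in both arms**
- Affected subjects per arm: 166 × 0.15 = 24.9.
- All placebo events: 0.80 × 166 × (0.85 + 0.15 × 98/196) = 0.80 × 166 × 0.925 = 122.8. Active: 0.52 × 166 × 0.925 = 79.8.
- Uncounted placebo events: 24.9 × 14/196 × 0.80 = 1.4, or 2.8 with a 28-day gap. Active: 0.9 and 1.8.
- Subject-days left in each denominator: 24.9 × 14 = 349, or 24.9 × 28 = 697.
- Both arms lose the same fraction, so the ratio stays 0.650.

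**Constant rate, assumed 10% placebo and 20% active dropout**
- Mean exposure: placebo 0.9 × 196 + 0.1 × 98 = 186.2 days; active 0.8 × 196 + 0.2 × 98 = 176.4 days.
- 14-day gap: 0.65 × (1 − 0.2 × 14/176.4)/(1 − 0.1 × 14/186.2) = 0.645.
- 28-day gap: 0.65 × (1 − 0.2 × 28/176.4)/(1 − 0.1 × 28/186.2) = 0.639.
- With the dropout rates reversed: 0.656 and 0.661.

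**PEx clustering before withdrawal, assumed 3 to 5 times the usual rate in the gap**
- Equal 15% dropout: 4.3 to 14.2 placebo events uncounted. The ratio stays 0.650 if clustering is the same in both arms.
- Dropout 10%/20% and no effect on the underlying rate: the ratio is 1.016 to 1.063 with all events counted, and 0.983 to 0.992 after the cut.

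**The case against.** The strongest reply is that the SAP already counts these events. The last paragraph of 9.2 counts qualifying PEx at unscheduled visits, Section 4.1 treats a PEx recorded at an Unscheduled Visit as if it came from a Possible PEx Visit, and Sections 5.1.1 and 13 run to discontinuation. On this view the last-visit sentences only name the final scheduled visit for outcomes such as FEV1 and CFQ-R. This reading is reasonable, and it means that one cannot say events *will* be lost. It does not remove the conflict. The withdrawal sentence covers efficacy assessments without limiting itself to by-visit outcomes, and the later paragraph is worded as a restriction and does not claim to override it.

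A reader might also infer that adverse events before withdrawal disappear from the safety analysis. The SAP does not establish that. Section 11.1 defines treatment-emergent events by onset between first and last dose, without reference to a visit, and Section 11 keeps unscheduled visits only out of the by-visit tables. What stands is that the safety wording in 9.2 sits awkwardly beside Section 11.1.

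A reader might further infer material bias towards the drug. For example, if 15% of placebo and 30% of active dropouts had a PEx in the gap, the ratio would be (79.8 − 7.5)/(122.8 − 3.7) = 0.61. The arithmetic is right, but nothing in the SAP supports those percentages or that direction, and they are applied to all dropouts.

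**Conclusion.** The contradiction holds as a conflict of end dates without a rule of precedence, and it reaches the primary event count, the exposure term and the time-to-first-PEx analysis. It is clearest for withdrawal of consent. For lost subjects the wording is less explicit.

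The expected effect is small: about 1-2% of placebo events at a constant rate, and no change in the rate ratio with equal dropout. The ratio moves by about 0.005 to 0.011 under the assumed 10%/20% split, in a direction set by which arm loses more subjects. A larger effect needs PEx to cluster before withdrawal and that burden to differ between arms, which is plausible but not shown by the document. The case for correction is that a rule feeding the primary endpoint can be derived in two ways, and that this should be settled before unblinding.

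**What to change.** Replace the two last-visit sentences in Section 9.2 with: *All data collected up to the date of consent withdrawal or last contact are included; a qualifying PEx with antibiotic start on or before that date counts.* Then:

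- limit the last-scheduled-visit rule to by-visit outcomes (FEV1, CFQ-R);
- state that treatment-emergent adverse events follow Section 11.1;
- name one end date per subject and use it for the PEx counting window (5.1.1), the log-exposure term (8.2.1, 9.4.1) and the censoring date (9.5.3).

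The last item needs a deliberate choice. If the common date is not the last dose, the denominator in Sections 4.2.1 and 8.2.1 changes for subjects who withdraw or are lost after stopping product, and Section 13 should say so.

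The cost is SAP wording and the matching derivations, with no new data. Section 2 bars sponsor changes after signature other than analyses requested by FDA, so this belongs before signature. Failing that, it should be reported in the CSR as a change from the SAP, as Section 14 provides.

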9.3. Adjustments for Multiplicity

The overall type I error rate will be controlled for primary and secondary efficacy outcomes with a fixed sequence, independent hierarchical assessment of efficacy.

The primary efficacy endpoint will be assessed first. If this comparison yields statistically significant results at two-sided alpha level of 0.05, then the secondary outcomes will be assessed in a hierarchical order for statistical significance.

The Type I error will be controlled for secondary efficacy outcomes with hierarchical assessments of efficacy at a two-sided alpha level of 0.05. If the assessment is not significant, then the analysis of the rest of endpoints will be exploratory. The order for tests for treatment effect in secondary efficacy endpoints is listed in [Section 4.2.2](#).

9.4. Primary Efficacy Analysis

9.4.1. Event Rate of New Pulmonary Exacerbations per Subject per 28 Weeks by Primary Definition

The primary efficacy endpoint is the event rate of new PEx per subject per 28 weeks using the primary definition (Sections [4.2.1](#) and [5.1](#)), for the comparison of lenabasum 20 mg BID cohort to the placebo cohort, in the mITT population, through Visit 8 (Week 28) which is the treatment period.

The event rate per subject per 28 weeks of new PEx will be compared between the lenabasum and placebo cohorts using a Poisson regression model with effects of treatment and log (subject treatment exposure duration), adjusting for baseline subject characteristics of site location (United States; other countries), number of new PEx requiring IV antibiotics in the previous year (1; 2; 3); FEV1 % predicted (< 70; \geq 70); and baseline CFTR-targeting medications use (Yes; No – taken concomitantly on Day 1, baseline), and based on the mITT population.

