4.2. Study Efficacy Endpoints

4.2.1. Primary Efficacy Endpoint

The primary efficacy endpoint is the event rate of new PEx per subject per 28 weeks using the primary definition of new PEx comparing the lenabasum 20 mg BID and placebo cohorts. The event rate is based on the occurrence of new PEx, and the occurrence will be assessed during the treatment phase. It is defined as follows:

The primary endpoint will be calculated by the following for each treatment cohort:

Event rate of PEx (per subject-28 Weeks) for a treatment group is calculated as follows:

Total number of PEx using primary definition during the treatment period / [sum of subject treatment exposure durations in the treatment group (days) / 196]

[figure not shown]
Event rate of PEx (per subject) for a treatment group (without adjustment of treatment exposure) is calculated as follows:

Total number of PEx using primary definition during the treatment period / number of subjects in the treatment group

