6.3. Sample Size and Power Considerations

The study is expected to enroll approximately 415 subjects, with ~166 subjects each in the lenabasum 20 mg BID and placebo BID cohorts and ~83 subjects in the lenabasum 5 mg BID cohort (accounting for an approximate 15% dropout rate). The study provides 80% power to detect a significant difference between the lenabasum 20 mg BID dose and placebo in the primary endpoint (PEx event rate) at a two-sided alpha of 0.05. This is based on an event rate ratio of 0.65 (a 35% event rate reduction in the lenabasum group), when the event rate in the control group is 0.80.

This also provides 90% power to detect a significant difference between lenabasum 20 mg BID and placebo BID in the secondary endpoint of time to first PEx. This is based on an estimate of the probability of an event (PEx) in the placebo group of 0.60, an estimated hazard ratio of 0.60 (risk reduction 0.40), and the probability of an event in the lenabasum group of 0.36.

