9.4.2. Sensitivity Analyses of Primary Endpoint Analysis

The following sensitivity analyses will be performed using the same statistical method as the primary endpoint analysis, including adjusting for baseline subject characteristics of site location (United States; other countries), number of new PEx requiring IV antibiotics in the previous year (1; 2; 3); FEV1 % predicted (< 70; \geq 70); and baseline CFTR- targeting medications use (Yes; No):

- The event rate per subject per 28 weeks of PEx will be compared between the lenabasum 20 mg BID and placebo cohorts using a Poisson regression model with effects of treatment and log (subject treatment exposure duration), based on the PP population.

- The event rate per subject per 28 weeks of PEx will be compared in the lenabasum 20 mg BID and placebo cohorts using a negative binomial model with effects of treatment and log (subject treatment exposure duration), based on the mITT population. Negative binomial regression is a generalization of Poisson regression which loosens the restrictive assumption that the variance is equal to the mean made by the Poisson model.
- The event rate per subject per 28 weeks of PEx will be compared in the lenabasum 20 mg BID and placebo cohorts using a negative binomial model with effects of treatment and log (subject treatment exposure duration), based on the PP population.

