9.5. Secondary Efficacy Analyses

The secondary efficacy endpoints ([Section 4.2.2](#)) will be summarized by treatment cohort. Actual values at each visit for each secondary outcome and changes from Baseline will be analyzed. The analyses and summaries of secondary efficacy endpoints will be performed on the mITT population. All secondary analyses will be at or through Visit 8, whichever is relevant, and will be done on observed values only. Two-sided p-values will be presented.

9.5.1. Event Rate per Subject per 28 Weeks of New Pulmonary Exacerbations by Secondary Definition

Analysis of endpoints for various event rates of PEx will be performed using the same method as the primary analysis in [Section 9.4.1](#).

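### The primary Poisson test names no variance estimator, so its 5% level and confidence intervals rest on variance equal to the mean

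*SAP*

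**What the plan says.** Section 9.4.1: the event rate will be "compared between the lenabasum and placebo cohorts using a Poisson regression model". The model has treatment, log exposure duration and four baseline factors. No scale parameter, robust variance, dispersion check or switching rule is given, so the default reading is the model-based Poisson variance.

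Section 9.3: "The overall type I error rate will be controlled for primary and secondary efficacy outcomes". The primary comparison is tested first at two-sided 0.05, and the secondaries follow in fixed order only if it succeeds.

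Section 9.5.1: "Analysis of endpoints for various event rates of PEx will be performed using the same method as the primary analysis". Three event-rate secondaries stand in the hierarchy of Section 4.2.2, two of them for 5 mg (83 subjects against 166).

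Section 9.4.2 adds negative binomial models as sensitivity analyses, because that model "loosens the restrictive assumption that the variance is equal to the mean made by the Poisson model". Section 9.5.2 extends them to the first secondary endpoint only, for 20 mg.

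Section 5.1.1 sets the gap rule for a new event: "Start date of new antibiotics for PEx is > 28 days after the stop date of any antibiotics given for any previous PEx". The clock runs from the prescribed course: "Stop date is the last day the physician prescribes that the subject should take this antibiotic treatment for a PEx".

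Section 4.2.1 divides events by "sum of subject treatment exposure durations in the treatment group (days) / 196".

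**The concern.** A model-based Poisson standard error is right only when the counts, given the covariates, have variance equal to their mean. Two features of this trial pull in opposite directions.

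- Subjects differ in their risk of PEx beyond what four factors explain. This pushes variance/mean above 1, and the test then rejects too often.
- After each event, no new event can count during the antibiotic course and the 28 days that follow, yet that time stays in the exposure. This pushes variance/mean below 1. The test is then conservative and its intervals are too wide.

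Exact cancellation would be a coincidence. At stake are the level of the test that opens the sequence, the level of three later tests, and the coverage of all their intervals.

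The negative binomial analyses would reveal over-dispersion, but they decide nothing and cannot represent variance below the mean. They also do not cover the 5 mg comparisons.

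**Working it through.** **Inputs from the SAP.** Two-sided alpha 0.05 (9.3). Placebo rate: "when the event rate in the control group is 0.80" (6.3). Rate ratio 0.65, so 0.80 × 0.65 = 0.52 on lenabasum. 166 per arm, 15% dropout, 80% power (6.3). Follow-up 196 days (4.2.1). No dispersion value or course length is given, so both are assumed below.

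**Step 1: reproduce the planned power.** With variance/mean φ, the log rate ratio has SE² = φ(1/0.80 + 1/0.52)/n = φ × 3.173/n, and |ln 0.65| = 0.4308.

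- n = 166 × 0.85 ≈ 141, φ = 1: SE = 0.1500, z = 2.872, power = Φ(2.872 − 1.960) = 81.9%. The stated 80% is reproduced on Poisson variance.
- n needed for 80% at φ = 1: 3.173 × (1.960 + 0.842)²/0.4308² = 134.2.
- Completers only: 80% holds up to φ = 141/134.2 = 1.05.
- Counting dropouts' exposure, with uniform dropout: effective n = 166 × (0.85 + 0.15/2) = 153.6, power 85.0%, and 80% holds up to φ = 153.6/134.2 = 1.14.

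**Step 2: size as a function of φ.** The true size of the nominal 5% test is about 2[1 − Φ(1.96/√φ)].

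| φ | 0.7 | 0.8 | 1.0 | 1.1 | 1.2 |
|---|---|---|---|---|---|
| Size | 1.9% | 2.8% | 5.0% | 6.2% | 7.4% |

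**Step 3: simulation of size.** Each subject has a gamma-frailty event process over 196 days. After each event, 42 or 49 days are blocked (28 plus an assumed course of 14 or 21 days). The null rate is 0.80 in both arms, with 15% uniform dropout. Assumed covariates: region 40/60 (rate ratio 1.1); prior PEx 50/35/15% (1/1.4/1.8); FEV1 below 70 in 50% (1.3); CFTR medication in 50% (0.75). The fit is a Poisson model with a log-exposure offset and a Wald test, over 8,000 trials per setting (Monte Carlo SE about 0.3 points). Entries are size in %, as Poisson / sandwich / leverage-corrected (HC3-type) sandwich.

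| Frailty variance | 166 v 166, 42 days | 166 v 166, 49 days | 83 v 166, 42 days | 83 v 166, 49 days |
|---|---|---|---|---|
| 0 | 1.9 / 5.3 / 4.7 | 1.6 / 5.1 / 4.6 | 1.8 / 5.3 / 4.4 | 1.6 / 5.5 / 4.6 |
| 0.5 | 3.6 / 5.2 / 4.6 | 3.3 / 5.0 / 4.6 | 4.0 / 5.7 / 4.9 | 3.6 / 5.8 / 5.0 |
| 1.0 | 6.1 / 5.8 / 5.2 | 4.6 / 5.2 / 4.7 | 5.3 / 5.4 / 4.6 | 4.8 / 5.5 / 4.7 |
| 1.5 | 6.9 / 5.1 / 4.6 | 6.1 / 5.3 / 4.7 | 7.6 / 5.7 / 4.7 | 6.0 / 5.2 / 4.5 |

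Pearson dispersion at 166 per arm ran from 0.70 to 1.18. A repeat run under the same assumptions (Monte Carlo SE about 0.4 points) gave Poisson about 1.2% to 7.4%, sandwich 4.8% to 6.4% and leverage-corrected 4.4% to 5.8%. A covariate-free simulation at 166 per arm (20,000 trials per scenario, 16 scenarios) gave 4.7% to 5.3% for the sandwich and 4.6% to 5.3% for a Pearson-scaled variance.

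**Step 4: power at rate ratio 0.65, 166 per arm** (4,000 trials, same order).

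- Most over-dispersed setting (42 days, frailty 1.5): 82.8 / 78.8 / 77.3%.
- Most under-dispersed setting (49 days, no frailty): 90.3 / 95.2 / 94.4%.

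The Step 1 formula with n = 153.6 and φ = 1.18 also gives 78.8%.

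**The case against.** The strongest reply is that no error has been shown. A conservative test still keeps its level, so below φ = 1 Section 9.3 is not breached and only power is lost. Size above 6% at 166 per arm needs residual frailty variance of at least 1.0, and 1.5 with 49 blocked days. Nothing in the SAP supports a figure that large, and the entry criteria on prior PEx (4.1.4) narrow the differences between subjects. Section 6.3 plans a 0.60 probability of at least one event on placebo, against 1 − e^(−0.80) = 0.551 under Poisson, which leans weakly toward under-dispersion. The SAP also discloses the assumption and prespecifies a check.

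Most of this stands, and it limits the point to a modest one. It does not remove it: the check does not decide the result, cannot represent under-dispersion and omits the 5 mg comparisons.

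Two stronger readings are tempting, and the documents support neither.

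- *That type I error is inflated.* Frailty alone, with variance 1.0 and no blocked time, would give 13.8%, but that ignores the gap rule in Section 5.1.1.
- *That the stated power leaves almost no room for over-dispersion.* The 1.05 limit treats dropouts as contributing nothing. Sections 4.2.1, 6.4.1 and 9.4.1 analyse all dosed subjects with their exposure, which moves the limit to about 1.14.

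**Conclusion.** The point holds as a gap in the specification. The 5% level and the intervals of the primary and event-rate secondary tests depend on variance equal to the mean, and the SAP neither supports that assumption nor protects against its failure. Under the assumed frailty and course lengths, the size of the 20 mg test is roughly 1% to 7%: conservative in most settings and modestly liberal at high frailty. The 5 mg comparison behaves similarly (1.6% to 7.6%). A robust variance brings both close to 5%. The direction in this trial cannot be known from the SAP. The change is a cheap improvement and does not correct a demonstrated error.

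**What to change.** Before the SAP is signed and the data unblinded, add to Section 9.4.1 that the primary test and 95% CI use a robust (sandwich) variance on the same Poisson model, with log exposure as an offset (coefficient fixed at 1, as the Section 4.2.1 rate implies). State in Section 9.5.1 that this applies to every event-rate secondary, including 5 mg. A small-sample (leverage) correction is optional. Keep the negative binomial as sensitivity. Timing matters because Section 2 bars sponsor changes after signature other than analyses requested by the FDA.

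The cost is one sentence and one code option; the rate ratio estimate is unchanged. At dispersion 1.18, power falls from 82.8% to 78.8% (77.3% with the correction), and part of the higher figure comes from a test running above its level. If counts are under-dispersed, power rises, for example from 90.3% to 95.2%. A robust variance does not repair any mismatch between first-to-last-dose exposure (8.2.1) and events counted after study product is stopped (9.2).

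Two separate corrections do not drive the error rate:

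- Prior IV-treated PEx is listed by the levels 1, 2 and 3 in Sections 9.4.1, 9.4.2, 9.5.3 and 9.5.4, but Section 13 makes it continuous. Choose one coding before unblinding.
- Section 4.1.9 has the stratification starting as 1 versus 2 or 3 and changing to 1 or 2 versus 3. Section 13 gives the reverse order. Reconcile them.
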